The Malezi I intervention was found to be feasible and acceptable as an integrated intervention within routine MNCH/PMTCT services. The internal Malezi I program evaluation, using a pre/post design, found substantial increases in caregiver knowledge and practices as reported through exit and household-based interviews. Knowledge among facility-based health providers and CHWs also increased significantly, and health providers reported increased access to ECD resources.

Given the existing and emerging evidence on potential strategies to better engage communities in supporting health promotion interventions, the Malezi II grant will expand Malezi I coverage of CCD program implementation to nearly double the number of facilities supported, and introduce additional components, specifically, a mass media campaign and video job aids. The addition of video job aids aims to further support and improve CHW education and counseling skills, and the addition of radio messaging aims to promote perceptions and knowledge of ECD, and possibly responsive caregiving behaviors, more broadly at the community level.

The Malezi II program, additional multi-media components, and theory of change model informing the evaluation

The Malezi II grant supports a continuation and expansion of the Malezi I CCD program described earlier, plus two additional interventions related to multi-media communications aimed at improving ECD perceptions, knowledge and responsive caregiver behaviors. These two approaches include a mass media communication strategy using radio messaging and the introduction of short video job aids, along with capacity building training for community health workers in the use of those job aids. This study is designed to evaluate the comparative effectiveness of the two interventions with respect to ECD perceptions, knowledge and responsive caregiving outcomes. In addition, by analyzing differences between baseline and endline within each study group (pre/post design), we will describe the effectiveness of radio messaging alone compared to no radio messaging, and the effectiveness of a fully integrated ECD intervention, including radio messaging, short video job aids and Malezi CCD program support compared to CCD program support without radio and short video support.

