- To what extent does the Malezi II radio messaging reach caregivers of young children?
- To what extent are caregiver ECD perceptions, knowledge and reported parenting practices changed after introduction of Malezi II radio messaging to their communities?
- Is there a relationship between reported listenership and/or message recall (dose) and caregiver ECD perceptions, knowledge and reported parenting practices?
- To what extent does exposure to the Malezi II full intervention (MRV-CCD: radio messaging, video job aids, continued CCD program support) improve caregiver knowledge and parenting practices?
- Does exposure to the Malezi II full intervention (MRV-CCD) improve caregiver knowledge and parenting practices significantly more than exposure to radio messaging alone (MR)?
- To what extent do the CHWs adhere to the Malezi II training with regard to use of the video job aids, delivery of complete and accurate ECD messages, and general quality of counseling support?
- Do the Malezi II video job aids improve the quality of CHW ECD counseling support given to caregivers in clinic and home settings?

METHODOLOGY

This study is a two-arm quasi-experimental pre-post evaluation design, comparing two interventions to establish their relative impact on caregiver knowledge and behaviors/practices among a cohort of caregivers of children 0-24 months at enrolment (baseline) and under three years after a 9-month

intervention exposure period (endline). In addition, the quality of counseling support to caregivers, at health facilities and through home visits, will be assessed at baseline and endline in a cohort of CHWs recruited from the MRV-CCD full intervention group. Figure 2a provides an overview of the research design for objectives 1 and 2. Figure 2b provides an overview of the research design for objective 3.

[figure not shown]

Figure 2a. Research design overview – community component

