The radio messaging in both intervention groups, and the short videos in the second intervention group (only) will be introduced after the baseline assessment of the caregiver cohort. The exposure period for the two interventions, as described in Table 2, will be for nine months, followed by the endline assessment of caregivers.

Table 2. Description of intervention packages in two study arms

Intervention group	Description and expected exposure (dose)
Malezi II minimum package Radio (MR)	Radio messaging spots Dose: Up to 35-40 different messages, 3 stations aired on (2 regional, 1 national), about 10 times per day; 7 days per week airing frequency; 9 months duration of exposure 
▪ Caregiver exposure to radio messaging during 9-month period: currently unknown, but estimated at 50% of caregivers hearing about 7 messages/week.
Malezi II full package Radio, Video Job Aids, CCD program (MRV-CCD)	Radio messaging spots 
▪ Same as MR group

MRV-CCD	
Short video ECD job aids (with training)
 
Five short ECD mobile films (videos) of 3-5 minutes each will feature a mixture of real-life testimonies and scripted interactions between health workers and caregivers, and demonstrations of caregivers stimulating their young child. Each video will show a range of age-appropriate ECD practices that encourage child development (play; communication; positive caregiver-child interaction; safe/stimulating environment; positive discipline), illustrating skills and providing knowledge. All videos will have some cross-cutting content, emphasizing the general benefits of ECD activities during the early years, and one video will be devoted exclusively to cross-cutting parental guidance on developmental milestones and benefits of applying ECD practices. Four videos will target specific age groups (0-5, 6-11, 12-23, >=24 months).
 
Caregiver exposure to group counseling at clinic is estimated to be 2-4 sessions in a 9-month period
 
Caregiver exposure to individual counseling at home is estimated to be 3-6 sessions in a 9-month period

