MRV-CCD	
Malezi I CCD program established (2016-17), with continuing technical and M&E supervision
 
 ▪ ECD (CCD-based) knowledge and education/counseling skills training (4 days didactic and practice) to facility-based and community health providers, including translated CCD-based manual with job aid ▪ M&E tools and refresher training ▪ Continuing joint quarterly supportive supervision to Malezi-supported facilities and CHWs with government health authorities ▪ Creative toy building training to support sustainable replenishment of toys for ECD sessions ▪ Toys (mostly home-made or safe household objects) and play mat for use in facility group sessions and home visits ▪ Materials for CHW work in facilities and homes: 
 ○ CCD participants' manual ○ CCD counseling card or new developed Flipbook which is a pictorial modified CCD counseling card ○ A bag of age appropriate play materials

The methodologies of each intervention arm have been tested independently (although not in a combined package) in high income countries and in some LMIC, showing varying degrees of effectiveness in changing caregiving behaviors (16). This research is therefore not an efficacy study, but instead tests the real world effectiveness of the additional value added from multi-media interventions. The Malezi Radio (MR) intervention group will assess the effectiveness of a *mass media communications strategy* targeting caregivers in communities, without having built the capacity of the health care system to reinforce ECD messaging and responsive caregiving skills. The Malezi Radio, Video and CCD (MRV-CCD) intervention group will assess the effectiveness of *adding mass media communication and CHW-capacity to use short ECD video job aids* in the context of a health care system with an established CCD program.

Location

The research study will be implemented in four selected districts of Tabora region. Recruitment of MRV-CCD intervention participants will take place in Malezi health facility catchment areas of Nzega and Igunga districts, while recruitment of the MR intervention participants will be done in districts outside of the Malezi program areas, Kaliua and Uyui districts.

[figure not shown]

Figure 3. Tabora Region and Districts

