Descriptive statistics (range, median, mean, percent) will be used to review the data overall and describe participant background characteristics, radio listenership patterns and parenting perceptions, knowledge and practices, identifying any baseline differences in population by study group. Confidence intervals (CI) will be calculated around summary measures and statistical tests of significance (non-parametric) will be applied where appropriate to compare the distribution of characteristics or outcomes across study groups. The effects of radio exposure only (objective 1) will be described by comparing study outcomes at baseline and endline within the MR study group only. Within study group differences in study outcomes will be described comparing distributions of responses to key outcome variables at baseline and endline using statistical testing appropriate for paired groups such as the paired t-test, Wilcoxon or McNemar's tests. Regression modelling may be used to estimate the intervention effect while controlling for covariates.

The additional effects of the combined exposure to radio, short videos and Malezi CCD (MRV-CCD; objective 2), as compared to the radio only effect, will be described using a differences in differences (DID) analysis. The treatment effect can be found by obtaining the proportion of caregivers with the outcome in the MRV-CCD and MR groups at both time periods. The difference in outcomes between study groups at both time periods may be charted to visualize the DID as shown in Figure 4, whereby the DID is what remains after subtracting the baseline differences between the two groups from the endline differences (30-5% = 25%). This will give an estimate of the extent of the improvement by the Malezi II full intervention. We will use regression modelling to estimate the intervention effect while controlling for covariates. We will use the following general form model:

$$Y = \beta_0 + \beta_1[\text{Intervention}] + \beta_2[\text{Time}] + \beta_3[\text{Intervention} \cdot \text{Time}] + \beta_4[\text{Covariates}] + \varepsilon$$

The interaction term coefficient β_3 will also estimate the extent of the DiD.

[figure not shown]

Figure 4. Differences in differences analysis graphic

Objective 3: Community Health Worker Cohort

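### The MRV-CCD pre-post change is described as the full package against CCD alone, but that reading needs an unstated assumption that outcomes would stay flat for nine months under continuing CCD

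*Protocol*

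**What the plan says.** The statement is in the protocol's Background, under *The Malezi II program, additional multi-media components, and theory of change model informing the evaluation*. There, "by analyzing differences between baseline and endline within each study group (pre/post design), we will describe the effectiveness" of two things. For the MRV-CCD group it is the integrated package of radio messaging, short video job aids and "Malezi CCD program support compared to CCD program support without radio and short video support". The Intervention Description repeats the intent: the MRV-CCD group is to assess the effect of adding mass media and video-aided CHW capacity "in the context of a health care system with an established CCD program".

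The Methodology section describes the comparators available: "This study is a two-arm quasi-experimental pre-post evaluation design, comparing two interventions". The arms are MR (radio, no CCD) and MRV-CCD (radio, videos and CCD). No arm has CCD alone.

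The Data Analysis section, Objectives 1 and 2, handles within-group change by "comparing distributions of responses to key outcome variables at baseline and endline using statistical testing appropriate for paired groups", with the paired t-test, Wilcoxon and McNemar's test as examples.

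The Intervention Description also says what happens between the surveys. Radio and videos begin after the baseline assessment. CCD, set up in 2016-17, goes on with quarterly supportive supervision. Table 2 adds "Caregiver exposure to individual counseling at home is estimated to be 3-6 sessions in a 9-month period", together with 2-4 group sessions at the clinic.

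**The concern.** A paired comparison inside one arm measures all change in the same caregivers between two dates. In MRV-CCD that change has several possible sources: radio, videos, nine more months of CCD contact, and children who are nine months older. The Background sentence assigns the change to radio and videos alone, by treating the baseline survey as CCD without them.

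The baseline survey shows what CCD had achieved by that date. The comparator named in the sentence is what CCD alone would have achieved by endline. The two are equal only if the trajectory under continuing CCD is flat.

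At stake is what the trial may conclude about radio and videos as an addition to CCD. The Policy/Program Significance section links the videos' contribution to caregiver behaviours with the possible scale-up of digital job aids. A rise in MRV-CCD, read as the Background sentence invites, could be credited to the media components although continuing CCD produced some or all of it.

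**Working it through.** **1. Can the planned contrasts deliver the stated comparison?**

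- MRV-CCD endline minus baseline = (radio + videos) + (nine further months of CCD) + (child ageing and calendar trend). This equals radio + videos only if the last two terms are zero.
- The difference-in-differences of MRV-CCD against MR removes radio and any trend common to both arms. What remains is videos and CCD together, so it does not give radio + videos over CCD.
- Covariate regression inside MRV-CCD does not separate the components, because every MRV-CCD community receives radio and videos after baseline on top of CCD.

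**2. Reproducing the plan's figures.** Inputs: n = 430 per group, MRV-CCD 25% to 45%, MR 10% to 15% (Table 4); correlation 0.4 (Sample Size Calculations, Objective 1, stated for MR and assumed here for MRV-CCD); 5% level, taken as two-sided because the protocol does not say. For the large-sample McNemar test with d = p2 − p1:

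- p11 = p1·p2 + ρ·√[p1(1−p1)·p2(1−p2)]
- discordant proportion D = p1 + p2 − 2·p11
- power = Φ{(√n·d − 1.96·√D) / √(D − d²)}

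MR, 10% to 15%: p11 = 0.0578, D = 0.1343, power = Φ(0.877) = 81% (Table 4: 81%). MRV-CCD, 25% to 45%: D = 0.3027, power above 99.9% (Table 4: >99%). Inflation: 430 × 1.2 / 0.85 = 607, as stated.

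**3. Rejection of no change when radio and videos add nothing.** The same formula is used with n = 430 and p1 = 25%, and p2 raised only by an assumed drift under continuing CCD. Both tails are counted. Worked case, 5 points at ρ = 0.4: p11 = 0.1544, D = 0.2413, Φ(0.152) = 56%.

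| Assumed drift | ρ = 0.4 | ρ = 0 |
|---|---|---|
| 0 points | 5% | 5% |
| 2 points | 14% | 10% |
| 3 points | 25% | 17% |
| 5 points | 56% | 37% |
| 10 points | 98% | 89% |

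The drift column is assumed throughout. At zero drift the test keeps its nominal level. A drift of about 2 points roughly doubles it or more.

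**The case against.** The strongest defence has four parts.

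- **The sentence is descriptive.** It sits in the Background, says the study will describe effectiveness, and writes out no null hypothesis. The contrast is not among the aims, numbered objectives or research questions. The research question on MRV-CCD asks how far exposure to the whole package, continued CCD included, improves outcomes, and the primary hypothesis is full package against radio alone. This stands. A reader might infer that Objective 2 or its difference-in-differences is invalid, or that the analysis section commits the sponsor to reporting the paired test as the added value of radio and videos. Neither follows: the Data Analysis section says no such thing, and Objective 2 does not claim to isolate the media components.
- **Baseline is measured under CCD, before radio and videos.** This also stands. The reading has a basis; what is missing is the flat-trajectory assumption on which it depends.
- **No drift figure exists.** The Sample Size Calculations report changes of 10-30 points, but those followed the introduction of CCD from a pre-CCD baseline. It is tempting to carry that range over and say that false attribution is near certain. The documents do not support this, because further sessions in an established programme may do much less.
- **Accumulated CCD dose cannot be computed.** The Table 2 session counts cover the study's nine months and are listed with the videos. The visit schedule varies with child age, and caregivers may have met CCD in pregnancy or through older children. The counts show that CCD contact continues; they do not support a before-and-after dose figure.

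None of this rescues the wording, which claims a comparison that the design cannot make without the unstated assumption.

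**Conclusion.** The point holds as a fault in a stated claim. The MRV-CCD pre-post change is the total change under continuing CCD plus radio plus videos. It measures the package against CCD alone only if the same caregivers' outcomes would have stayed flat for nine months, which the protocol neither states nor supports. No other planned contrast fills the gap.

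The size is unknown. If radio and videos add nothing, the chance of a significant rise or fall goes from 5% at zero drift to 56% at 5 points and 98% at 10 points (37% and 89% at zero correlation), given 430 effective pairs, a 25% baseline and a two-sided 5% test. These figures show sensitivity to drift and do not predict the trial's error rate. The correction is worth making because it changes what may be concluded and costs almost nothing. It does not touch the sample size or the primary comparison with MR.

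**What to change.** **Wording (sufficient alone).** In the Background section on the Malezi II program and in the Intervention Description, state that the MRV-CCD pre-post change is the total change under continuing CCD plus radio plus videos, and that it does not isolate what radio and videos add to CCD. The cost is a weaker claim.

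**Optional exploratory sensitivity analysis.** Inside MRV-CCD, compare outcomes at endline with outcomes at baseline for index children of the same age (about 10-24 months, where the two rounds overlap). Regress on survey round and child age in months, with standard errors clustered by caregiver and enumeration area. Restrict it to sites where CCD is long established. The Intervention Description says the areas have had CCD since 2016, but the Background plans nearly double the facilities, and the site selection criteria do not require Malezi I status.

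State its assumptions: no calendar trend, and no effect on endline answers of the earlier interview, the toy offered at baseline or the observed home visits that some caregivers receive. Leave out toy-in-home items, since a toy in the home is one of the indicators used for sizing.

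The data are already collected, so the cost is one regression and lower precision: with ages spread evenly over 0-24 months, about 14/24 (58%) of caregivers contribute at each round. It should not be presented as recovering the radio-plus-video effect.

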The outcome parameters used for sample size calculations for objectives 1 and 2 are estimated from the Malezi I program evaluation baseline data (before introduction of CCD program), comparable to what we would expect in the MR intervention group, who have not been exposed to any CCD intervention. From 24-29% of caregivers reported having a local or shop toy in the home, 22% reported singing to the child in the past month, and 7-13% reported reading or writing with the child in the past week.

Objective 1: To determine caregiver radio listenership patterns at baseline, and exposures to the ECD radio messaging nine months' post-intervention, and effect of radio exposure on caregiver ECD perceptions, knowledge and reported parenting practices, using pre-post surveys in a cohort of caregivers of children 0-24 months of age at baseline, in study communities from each intervention arm.

A sample size of 593 enrolled in the MR intervention group will provide 80% to detect a 5% or greater change from baseline (10%) to endline (15%) in the MR intervention group, taking into account 15% LTFU, design effect of 1.2, and estimated correlation of 0.4 between respondents at baseline and endline (Table 3). This sample size will provide even greater power to detect a 10% difference if baseline estimates are higher than 10%.

Table 3. Sample size estimation* parameters, MR group, caregiver cohort, pre-post

Arm	Prevalence of key outcome			Power	Sample size	Adjusted Sample size (15% LTFU, DE 1.2)
	Baseline	Endline	Expected Change			
MR (Malezi radio)	10%	15%	5%	80%	420	593
	20%	30%	10%	99%	419	592
	25%	35%	10%	98%	411	580

*STATA 14 paired proportions large-sample McNemar's test at 5% level significance.

Objective 2: To determine whether the Malezi II full intervention (MRV-CCD) significantly increases caregiver's knowledge and parenting behaviors/practices when compared to radio messaging alone, using a pre-post quasi-experimental evaluation design in a cohort of caregivers of children 0-24 months of age at baseline, in MRV-CCD and MR communities.

The change between baseline and endline in the Malezi I evaluation for the above-mentioned indicators ranged from 10-30% after introduction of the Malezi I CCD program. With the introduction of radio messaging only, we estimate a 5-10% effect size, and about a 20-30% effect size in the full intervention (MRV-CCD) group (Table 4).

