We estimate that a sample size of n=430 caregivers per intervention group will provide 90% power to detect a 15% "difference-in-differences" between the MR and MRV-CCD intervention groups at endline, and >80% power to detect a 5% change in the MR intervention group, and a 20% change in the MRV-CCD intervention group between baseline and endline, at a level of 5% significance. Taking into account a 15% non-retention rate and a design effect of 1.2, we will aim to enroll 1214 into the caregiver cohort or n=607 in each intervention group.

Table 4. Sample size estimation* parameters, MR compared to MRV-CCD groups, caregiver cohort, pre-post and differences-in-differences

Arm	Prevalence of key outcome			Power	Sample size	Adjusted Sample size (15% LTFU, DE 1.2)
	Baseline	Endline	Expected Change			
MR (Malezi radio)	10%	15%	5%	81%	430	607
MRV-CCCD (Malezi radio + radio + CCD program)	25%	45%	20%	>99%	430	607
Difference	15%	30%	15%	90%	860	1214

*Sample Size and Power estimated by a simulation of the DID Analysis using R Software Package.

Objective 3. To determine whether the introduction of short video job aids (training, provision, supportive supervision) to the Malezi II CCD program improves the quality of counseling provided by the CHW in the clinic and the home, using pre-post observation fidelity checklists for all CHWs working in the MRV-CCD communities.

The Malezi I evaluation assessed CHW-reported time spent in the home providing ECD messages to pregnant women or caregivers of children under 5 at baseline (14-17%) and endline (64-74%). While the change was substantial, we estimate that the actual CHW counseling skills would be lower using an observation checklist compared to CHW self-reported behaviors. We conservatively estimate that CHWs in the MRV-CCD intervention group, already trained in the Malezi I CCD program, will score at 50% on the baseline observation checklists in this evaluation, increasing 15-20% after introduction and capacity building in using the short videos.

Table 5 shows that a sample size of 123 CHWs will achieve 80% power to detect a 15% change between baseline and endline in CHW quality of counseling checklist score, taking into account a correlation of 0.4 between measures, a 5% non-retention rate and a design effect of 1.1.

Table 5. Sample size estimation* parameters, MRV-CCD CHW cohort, pre-post

Arm	Prevalence of key outcome			Power	Sample size	Adjusted Sample size (5% LTFU, DE 1.1)
	Baseline	Endline	Expected Change			

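### Table 4's 90% power for the 15-point difference-in-differences does not follow from the protocol's inputs: on the protocol's own scale it is about 99.9%

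*Protocol*

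**What the plan says.** The Objective 2 paragraph of Sample Size Calculations states that "a sample size of n=430 caregivers per intervention group will provide 90% power to detect a 15" percentage-point DID between the groups, at 5% significance. Table 4 has three rows on that basis:

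- MR, 10% to 15%: n=430, power 81%
- MRV-CCD, 25% to 45%: n=430, power above 99%
- Difference, 15 points: 860 in total, power 90%

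The only method given is the table footnote: "Sample Size and Power estimated by a simulation of the DID Analysis using R Software Package". Loss and clustering are added after n=430: "Taking into account a 15% non-retention rate and a design effect of 1.2, we will aim to enroll 1214 into the caregiver cohort", or 607 per group.

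The correlation is given under Objective 1, which assumes a "design effect of 1.2, and estimated correlation of 0.4 between respondents at baseline and endline". It is not repeated for Table 4.

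Data Analysis, Objectives 1 and 2, fixes the scale of the effect. It says "The treatment effect can be found by obtaining the proportion of caregivers with the outcome" in each group at both times, and that "the DID is what remains after subtracting the baseline differences between the two groups from the endline differences", with an example that subtracts percentages (30-5% = 25%). It then introduces a regression with "We will use the following general form model" and says that the interaction coefficient "will also estimate the extent of the DiD".

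**The concern.** A change of 5 points from 10% is a small effect for 430 pairs. A DID of 15 points is three times as large, and its standard error is less than twice that of the MR change. If 430 per group gives 81% for the first, it should give far more than 90% for the second. Either the DID row was computed on a different basis from the other rows, or the simulation tested something other than the difference of proportions that the protocol defines.

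This is the stated power of the trial's between-arm comparison. The direction of the error depends on the scale. If the simulation was additive, power is understated and little is lost. If it tested an interaction on the logit scale, the comparison has much less power than stated. The protocol names no link function for its regression and gives no simulation settings, so a reader cannot tell which.

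**Working it through.** **Inputs.** From Table 4: n=430 per group, MR 10% to 15%, MRV-CCD 25% to 45%, 5% significance (taken as two-sided). From Objective 1: correlation r=0.4, carried over to Table 4 as an assumption and varied below.

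**Step 1: reproduce the rows that can be reproduced.** For MR at r=0.4:

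- P(yes at both times) = 0.10×0.15 + 0.4×√(0.09×0.1275) = 0.0578
- Discordant proportion = 0.10 + 0.15 − 2×0.0578 = 0.1343
- McNemar power = Φ[(0.05√430 − 1.96√0.1343)/√(0.1343 − 0.05²)] = Φ(0.877) = 81.0%, as stated

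The same method gives more than 99.9% for MRV-CCD, as stated. It also gives 80.1%, 99.0% and 98.0% for Table 3 (stated 80, 99 and 98). The inflation 430×1.2/0.85 = 607 agrees too.

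**Step 2: the DID row on the difference-of-proportions scale.** With q = 1 − p, the variance of one person's change is p₀q₀ + p₁q₁ − 2r√(p₀q₀p₁q₁).

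- MR: 0.09 + 0.1275 − 0.8×0.1071 = 0.1318
- MRV-CCD: 0.1875 + 0.2475 − 0.8×0.2154 = 0.2627
- SE of the DID = √[(0.1318 + 0.2627)/430] = 0.0303
- Power = Φ(0.15/0.0303 − 1.96) = Φ(2.99) = 99.9%
- With r=0: SE = √(0.6525/430) = 0.0390, power 97.1%

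Simulation of 20,000 paired data sets agrees: 99.9% at r=0.4 and 97.0% at r=0.

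**Step 3: can another correlation rescue the row?** For binary outcomes at these rates, r can lie between −0.140 and 0.793 in MR and between −0.522 and 0.638 in MRV-CCD. A common r therefore lies between −0.140 and 0.638. Across −0.13 to 0.63, DID power at n=430 runs from 95.2% to above 99.9%. Solving each row for its own n gives:

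| r | n for MR 81% | DID power at that n | n for DID 90% | MR power at that n |
|---|---|---|---|---|
| −0.13 | 796 | 99.85% | 344 | 46.1% |
| 0 | 706 | 99.85% | 305 | 46.0% |
| 0.2 | 568 | 99.86% | 244 | 45.9% |
| 0.4 | 430 | 99.86% | 184 | 45.7% |
| 0.6 | 292 | 99.87% | 124 | 45.2% |
| 0.63 | 271 | 99.87% | 115 | 45.1% |

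Rounding does not explain the gap. At r=0.4, MR power of 80.5–81.5% needs n of 425–436, and DID power of 89.5–90.5% needs n of 181–188. Over all the correlations tried, the smallest ratio of the two sample sizes is 2.24 to 2.29.

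**Step 4: can the design effect?** A common design effect only rescales n, so the table above still applies. Counting the stated 1.2 inside n=430 for the DID row alone gives 99.5% (r=0.4) or 94.0% (r=0). To reach 90% needs a design effect of 2.33 (r=0.4) or 1.41 (r=0).

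**Step 5: the logit alternative.** The odds ratios are 2.4545 (MRV-CCD) and 1.5882 (MR). Their ratio is 1.545, with log 0.4353.

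- r=0.4: SE 0.1997, power Φ(0.4353/0.1997 − 1.96) = 58.7%
- r=0: SE 0.2567, power 39.6%
- r=0.63: SE 0.1579, power 78.7%

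Simulation gives 58.2% at r=0.4 and 39.1% at r=0. So 90% is not reached on this scale either.

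**Step 6: what n=430 does detect.** On the additive scale at r=0.4, the DID detectable with 90% power is (1.96 + 1.2816)×0.0303 = 0.098, or about 9.8 points.

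**The case against.** The best defence is that a shared basis is inferred. The correlation of 0.4 is stated for Objective 1 and for the community health worker cohort, not for Objective 2. The DID row comes from a simulation whose settings are not shown, so it may have contained a variance component that the within-arm rows did not. With 12–16 facilities per group, 430 caregivers are about 27–36 per facility. A variance inflation of 2.33 would then correspond to an intracluster correlation of roughly 0.04–0.05 (1.33/35 to 1.33/26).

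Part of this stands: the cause cannot be identified, and an undisclosed component cannot be excluded. It does not rescue the figure. The result does not depend on r=0.4, because every common correlation tried misses 90%. The inflation needed (1.41 to 2.33) exceeds the stated design effect of 1.2, which the protocol applies after n=430.

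A second objection is that the logit case is conjecture, since the Data Analysis text points to the additive scale. That is fair. The logit case is only conditional and does not explain the 90%. It shows why the scale should be stated.

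A third is that nothing in the design changes. This also stands on the additive scale: the error is conservative, and the MR row remains the lowest-powered in Table 4.

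**Conclusion.** The concern holds. On the difference-of-proportions scale that the protocol defines, 430 per group gives 99.9% power for the 15-point DID at a correlation of 0.4, and 97.1% with no pairing, against the stated 90%. Put the other way, 90% power would need only about 184 per group at r=0.4, and at that n the MR row would have 45.7%.

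This rests on a two-sided 5% test, the Table 4 rates, and no variance beyond the stated design effect. On that basis the sample is not shown to be too small. On a logit interaction, power would be 58.7% at r=0.4, and 90% would be a substantial overstatement. The figure should be corrected because it is the stated power of the between-arm comparison and no common basis consistent with the protocol's stated inputs and additive scale produces it.

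**What to change.** Re-run the simulation on the risk-difference scale, with every row of Table 4 on one basis: correlation 0.4, and loss and design effect applied once. Then either restate the DID power (expected above 99%) or keep 90% and give the DID it can detect, about 10 points. State in the Objective 2 text the scale, correlation, loss and clustering used. If the simulation did test a logit-scale interaction, say so and reconcile it with the difference-of-proportions definition in Data Analysis.

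The cost is one simulation and a few lines in the Objective 2 paragraph and Table 4, with no change to enrolment on the additive scale. The possible downside is that, if a logit interaction turns out to lie behind the figure, the 90% must be lowered or replaced by the risk-difference result.
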